5.1 Primary objective

To evaluate the safety of DSP-5423P (40-80 mg/day) for 52-week treatment.

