15.1 Target sample size

Number of subjects enrolled: 200 subjects

- Number of subjects treated with DSP-5423P for 6 weeks and more in cohort 1: 50 subjects
- Number of subjects treated with DSP-5423P for 52 weeks in either cohort 1 or cohort 2: 100 subjects

The new enrollment can be terminated at the time when 100 subjects with 52-week exposure of DSP-5423P are collected, together with a separate confirmatory study [Confirmatory Study of DSP-5423P in Patients with Schizophrenia <Phase 3> (protocol: D4904020)].

Rationale

Based on the guideline, THE EXTENT OF POPULATION EXPOSURE TO ASSESS CLINICAL SAFETY FOR DRUGS INTENDED FOR LONG-TERM TREATMENT OF NON-LIFE-THREATENING CONDITIONS dated 24 May 1995, 100 subjects with one year (52 weeks) exposure of DSP-5423P will be collected in cohort 1 and 2. In addition, to investigate the safety and efficacy of switching DSP-5423 (tablet) to DSP-5423P, approximately half of the target number of subjects will be enrolled in cohort 1 as subjects who switched DSP-5423 (tablet) to DSP-5423P. Considering approximately half of enrolled subjects early terminated in previous studies of DSP-5423 (tablet),

target number of subjects was set to 200. No statistical consideration was applied.

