6.1 Safety analysis population

Subjects with at least one application of DSP-5423P.

Efficacy analysis will also be performed based on the safety analysis population.

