9.12.1 Adverse event

The adverse event will be coded using the Medical Dictionary for Regulatory Activities (MedDRA), Version 19.1. Treatment-emergent adverse event (TEAE) is defined as adverse events with start date on or after Day 1. Regardless of cohort, adverse events occurred on same date as the initial date of application of DSP-5423P will be defined as TEAE. All adverse events, regardless of TEAE or not, will be listed. A treatment-related TEAE is defined as a TEAE for which the causal relationship to the study treatment is either ‘definite’, ‘probable’, or ‘possible’.

The summary of TEAE will include the number of event, and the number and percentage of subjects which are classified in the following TEAE or treatment-related TEAE categories. Extrapyramidal (EPS) adverse event will be defined based on MedDRA PT and determined at blinded data review meeting. The skin-related adverse event will be defined as an adverse event

with any application sites collected on EDC.

- Adverse event (any TEAE)
- Death (TEAE leading to death)
- Serious adverse event (serious TEAE)
- Adverse event leading to treatment discontinuation
 - (TEAE leading to treatment discontinuation)
- Severe adverse event (severe TEAE)
- Extrapyramidal adverse event (extrapyramidal TEAE)
- Skin-related adverse event at the application site (skin related TEAE)

The number and percentage of subjects who have TEAE or treatment-related TEAE will be summarized by SOC/PT for each cohort. If a subject has multiple events categorized in same SOC/PT, the subject will be counted only one time into the SOC/PT. SOCs are sorted by alphabetically and PTs are sorted within SOC in descending order of frequency of cohort total. If there are ties, PTs are sorted by alphabetically. TEAE leading to treatment discontinuation will be summarized in the same manner.

Common TEAE are PT of TEAEs experienced by 2% or more subjects in cohort total. Common TEAE and common treatment-related TEAE will be summarized by SOC/PT.

The number and percentage of subjects who have TEAE or treatment-related TEAE will be summarized by SOC/PT and maximum severity. For this summaries, if a subject experienced more than one episode of a TEAE within a PT, the subject is counted only once in the PT at the maximum severity. If the maximum severity is missing, the episode will be kept as missing (not specified). In determining maximum severity, severities are ranked from missing (not specified), mild, moderate, to severe.

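### The headline adverse-event tables give crude percentages of patch-treated subjects, and no planned output gives an exposure-adjusted rate or a 52-week cumulative risk, although the plan expects heavy drop-out

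*SAP*

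**What the plan says.** Protocol 5.1 gives the primary objective: "To evaluate the safety of DSP-5423P (40-80 mg/day) for 52-week treatment". Protocol 15.1 sets the targets as "Number of subjects enrolled: 200 subjects" and "Number of subjects treated with DSP-5423P for 52 weeks in either cohort 1 or cohort 2: 100 subjects". It links the two by expected attrition, "Considering approximately half of enrolled subjects early terminated in previous studies of DSP-5423 (tablet"), and adds "No statistical consideration was applied".

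SAP 6.1 defines the safety population as "Subjects with at least one application of DSP-5423P". SAP 9.12.1 adds "Treatment-emergent adverse event (TEAE) is defined as adverse events with start date on or after Day 1". The definition sets no end date, and SAP 7.2.1 collects events up to the follow-up visit. The headline summary follows: "The number and percentage of subjects who have TEAE or treatment-related TEAE will be summarized by SOC/PT for each cohort". The overview table, the severity tables and the subgroup tables (SAP 9.12.8) use the same kind of percentage.

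SAP 9.12.1 also plans tables by time of first onset, running to Week 40 or later, in which each period's denominator is the subjects treated with the patch in that period. SAP 10.2 lists them as Tables 14.3.1.6 to 14.3.1.9, 14.3.1.25 and 14.3.1.26. They cover all, common, treatment-related, extrapyramidal and skin-related TEAEs.

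Kaplan-Meier is planned for treatment discontinuation only (SAP 9.11.4 and 10.1). Neither the SAP text nor its output list contains subject-years at risk for adverse events, an incidence rate, a cumulative incidence, or a confidence interval for any adverse-event proportion.

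**The concern.** A percentage of everyone ever given a patch, in a 52-week study, is easily read as the 52-week risk. If many subjects leave early, they add a full unit to the denominator but only part of a year of observation. The figure then depends on the drop-out pattern as well as on the drug, and most of all for events that start late, which a one-year study exists to find.

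The same dependence affects comparisons across the two cohorts and across subgroups if their drop-out differs. Cohort 1 reaches the patch after six weeks on tablets and Cohort 2 does not, so a difference is plausible. It also affects which terms pass the crude 2% threshold for the common-TEAE tables.

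**Working it through.** **The plan's own figure.** 100 / (1 - 0.5) = 200. The enrolment target reproduces exactly from 100 subjects with 52-week exposure and 50% attrition.

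**Assumptions.** The documents give no TEAE risk, event timing or drop-out shape. I take a true 52-week risk R of 20%, drop-out D between 30% and 60% by Week 52, and drop-out independent of events. The target is the risk had all subjects stayed on treatment.

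**Constant hazards.** Per 52 weeks, l = -ln(1 - R) and d = -ln(1 - D). The crude percentage is l/(l + d) × [1 - exp(-(l + d))], with l = 0.2231 for R = 20%.

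- D = 30%: d = 0.3567; 0.2231/0.5798 × (1 - 0.56) = 16.9%
- D = 40%: d = 0.5108; 0.2231/0.7340 × (1 - 0.48) = 15.8%
- D = 50%: d = 0.6931; 0.2231/0.9163 × (1 - 0.40) = 14.6%
- D = 60%: d = 0.9163; 0.2231/1.1394 × (1 - 0.32) = 13.3%

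At D = 50%, a true 10% appears as 7.3% and a true 40% as 29.7%. Adding two weeks of post-treatment follow-up moves 14.6% only to 15.0%.

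**Timing of events (R = 20%, D = 50%).**

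- All events in Weeks 1-6: drop-out hazard in that window is 0.6931 × 6/52 = 0.0800; 0.2231/0.3031 × (1 - 0.8 × 0.9231) = 0.1925, about 19%.
- All events after Week 26: 0.2231/0.5697 × (1 - 0.8 × 0.7071) × 0.7071 = 12.0%.
- With front-loaded drop-out (proportion remaining 0.5 raised to the square root of t/52, integrated numerically), these become 17.2% and 11.1%.

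**What the first-onset tables recover.** Take 200 patch-treated subjects, R = 20%, D = 50% and constant hazards. The four 13-week periods have about 10.0, 7.9, 6.3 and 5.0 first onsets over 200, 168, 141 and 119 subjects treated: 5.0%, 4.7%, 4.5% and 4.2%. These sum to 18.4% and chain to 17.2%, so part of the gap from 14.6% to 20% is recovered. Two things hold them below 20%. Subjects who already had the event stay in later denominators. Subjects who leave during a period count as if treated throughout it; removing prior events alone would give 18.5%. For late-only events, the last two periods would show about 9.7% and 8.7%, chaining to 1 - 0.9029 × 0.9132 = about 17.5%, against a crude 12.0%.

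Three limits remain by design. The listed periods overlap (Weeks 1-6 lie within Weeks 1-13). An event after the last patch can enter a numerator without its subject being in the denominator. No onset table is listed for serious TEAEs or TEAEs leading to discontinuation.

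**Common-TEAE threshold.** By the same formulas at D = 50%, a term with a true risk of 2.5% (constant hazard), or of 3% arising only after Week 26, shows as about 1.8% and falls below the 2% cut.

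**The case against.** A reader might infer that TEAEs are reported only as crude percentages of all patch-treated subjects. The documents do not support that. The first-onset tables have denominators that shrink as subjects leave, and they expose much of any late risk.

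A reader might also infer that the crude figures simply understate risk. That needs a target and an assumption. For the probability of an event while on treatment, with discontinuation as a competing event, the crude percentage is essentially right once every subject has completed or stopped. Independent drop-out is doubtful too, since Protocol 7.2.3 says antipsychotics are often stopped for adverse reactions or lack of efficacy.

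The size can also be overdrawn. Protocol 7.2.2 reports that most of the common adverse events in Japanese tablet studies appeared within four weeks of starting; for such early events the shortfall is small. The figure of about half refers to enrolled subjects. Cohort 1 subjects lost in the tablet phase never enter the safety population, so drop-out in the actual denominator may be below 50%.

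Finally, the study is descriptive, the documents do not call these percentages 52-week incidence, and no cohort test is planned. Event counts (SAP 9.12.1) and exposure duration (SAP 9.9) are both summarised, so a reader could assemble a rough event rate for the overview categories.

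All of this stands, and it limits the point. It does not supply a cumulative 52-week figure, time at risk to first event, or any interval estimate.

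**Conclusion.** The point holds as a cheap improvement, not as an error that invalidates the safety analysis. The headline tables use a fixed denominator despite expected heavy attrition. The first-onset tables reduce the problem without closing it. No planned output gives the primary objective an exposure-adjusted rate or a 52-week cumulative risk, and the plan does not say which risk its percentages target.

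If the target is risk under continued treatment, the crude figure at 50% drop-out is about 0.96 of the true risk for events in Weeks 1-6, about 0.73 under constant hazards, and about 0.55 to 0.60 for events after Week 26. These ratios rest on independent drop-out and on assumed risks, timings and drop-out shapes. If the target is an event while on treatment, there is no material bias.

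**What to change.** Keep crude n (%) and the first-onset tables. Then:

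- In Table 14.3.1.1 and the common-TEAE table (14.3.1.3), by cohort and cohort total, add subject-years at risk and incidence per 100 subject-years. Count time to the first event or to the end of a stated TEAE window.
- For any, serious, extrapyramidal and skin-related TEAEs, add cumulative incidence at Weeks 28 and 52 with 95% CI. State whether discontinuation is censored (risk if treatment continued, assuming non-informative drop-out) or treated as a competing event.
- For TEAEs leading to discontinuation, use the Aalen-Johansen cumulative incidence with other discontinuations as competing events. One minus Kaplan-Meier would overstate the observable risk there.

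Onset and application dates are already collected, so the cost is SAP wording and a few columns. The downsides are that any censored estimate rests on the stated drop-out assumption, and that the displayed risk may look less favourable.

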Based on the approved dose of blonanserin tablet, the initial dose of DSP-5423 (tablet) was set at 8 mg/day and the dose was increased or decreased according to the maintenance dose (8-16 mg/day). Oral administration was planned after meal (in the morning and in the evening) in accordance with the approved treatment regimen of blonanserin tablet.

Since initial dose was set at 8 mg/day, it was considered necessary to determine the optimal dose

for 2 weeks. It has been reported that the treatment response assessment of antipsychotics should be performed 2 to 4 weeks after administration initiation ^{ref 11)}. Furthermore, in the clinical studies of DSP-5423 (tablets) conducted in Japan, most of the common/frequent adverse events, including akathisia, tremors, insomnia, and increased blood prolactin, have been observed in 4 weeks after administration initiation. Therefore, 6-week was set as the duration enough to collect effectiveness and safety data on DSP-5423 (tablet).

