4.2 Secondary objective

- To evaluate the safety and effectiveness of switching from DSP-5423 (tablet) to DSP-5423P.
- To evaluate the effectiveness and pharmacokinetics of DSP-5423P (40-80 mg/day) for 52-week treatment.

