one of following non-missing dates: end date of AE or date of the initial application date of DSP-5423P.

6. If both month and day (or only month) of start date is missing, and start date is not in the same year of initial application date of DSP-5423P, start date will be imputed as the first day (Jan01) in that year.

2) Prior/Concomitant Medication

End Date:

1. If ongoing is checked, no imputation will be performed.
2. If ongoing is not checked and end date is totally missing or year is missing, then end date will be imputed as the last visit date.
3. If only day of end date is missing, end date will be imputed as the earlier one of following dates: the last day of that month and the last visit date.
4. If both month and day (or only month) of end date is missing, end date will be imputed as the earlier one of following dates: the last day (Dec31) in that year or the last visit date.

Start Date:

1. If the medication is 'started prior to study' (checked in the CRF), no imputation will be performed (That medication should be defined as prior medication).
2. If the medication is not 'started prior to study' (checked in the CRF) and start date is totally missing, no imputation will be performed (That medication should be defined as neither prior medication nor concomitant medication).
3. If only day of start date is missing, start date will be imputed as the first day in that month.
4. If both month and day (or only month) of start date is missing, start date will be imputed as the first day (Jan01) in that year.

3) Initial/Current Episode of Schizophrenia

For the purpose of the estimation of Duration of illness and duration of current episode, the day of onset date of initial/current episode will be imputed according to the followings;

1. If onset date is totally missing, no imputation will be performed.
2. If only date of onset date is missing, onset date will be imputed as the first day in that month.
3. If only month of onset date is missing, and onset date is in the same year of informed consent, onset date will be imputed as previous day of informed consent.
4. If only month of onset date is missing, and onset date is not in the same year of informed consent, onset date will be imputed as June 30th.

9. Statistical Method

All efficacy, safety and other analysis are based on Safety Analysis Population, and PK analysis are based on PK analysis population. All subjects and data collected will be presented in listings.

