9.12 Safety Analysis

Safety analysis will be performed for each cohort and cohort total based on safety population, besides C-SSRS summaries only for each cohort.

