The number and percentage of subjects who have TEAE or treatment-related TEAE will be summarized by SOC/PT and first onset date. If a subject experienced more than one event within a PT, the subject is counted only once in the PT based on the earliest event started on the same or closer to Day 1. Denominator of percentage for each period of interest is the number of subjects who were treated with DSP-5423P in each period.

Onset: Day 1 to 7, Day 8 to 14, Day 15 to 28, Day 29 to 42; Week 1 to 6;
Week 1 to 13; Week 14 to 26; Week 27 to 39; Week 40 or later
(Week 1=Day 1 to 7, Week 2=Day 8 to 14)

As TEAE of interests, Extrapyramidal TEAE and skin related TEAE will be summarized by SOC/PT. Additionally, those TEAE will be summarized by maximum severity or first onset date in same manner as summaries of TEAE. In summary tables, the frequencies for entire TEAE related to extrapyramidal symptoms or TEAE related to skin, not just by SOC/PT, will be presented.

Adverse events and extrapyramidal adverse events started during DSP-5423(tablet) treatment period of Cohort 1, meaning Tab-Day 1 to Day -1 will be summarized by SOC/PT.

Listings for adverse events, AE leading to death, SAE, AE leading to treatment discontinuation, Extrapiramidal AE and skin related AE will be generated. Both TEAE and pre-treatment event which started before Day 1, will be included in those listings. In the listing for skin related AE, the application site will also be presented.

The adverse events during DSP-5423(tablet) treatment period of Cohort 1 will be listed.

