Table 14.3.1.18	Treatment-Emergent Adverse Events by System Organ Class and Preferred Term by Age	Safety Population
Table 14.3.1.19	Treatment-Emergent Adverse Events by System Organ Class and Preferred Term by Duration of Illness	Safety Population
Table 14.3.1.20	Treatment-Emergent Adverse Events by System Organ Class and Preferred Term by Hospitalization Status	Safety Population

No	Title	Population
	at Screening	
Table 14.3.1.21	Adverse Events in DSP-5423 (tablet) Treatment Phase by System Organ Class and Preferred Term	Subjects treated with DSP-5423 (tablet)
Table 14.3.1.22	Extrapyramidal Adverse Events in DSP-5423 (tablet) Treatment Phase by System Organ Class and Preferred Term	Subjects treated with DSP-5423 (tablet)
Table 14.3.1.23	Treatment-Emergent Extrapyramidal Adverse Events by Maximum Severity, System Organ Class, and Preferred Term	Safety Population
Table 14.3.1.24	Treatment-Emergent Adverse Events Related to Skin by Maximum Severity, System Organ Class, and Preferred Term	Safety Population
Table 14.3.1.25	Treatment-Emergent Extrapyramidal Adverse Events by First Onset Time, System Organ Class, and Preferred Term	Safety Population
Table 14.3.1.26	Treatment-Emergent Adverse Events Related to Skin by First Onset Time, System Organ Class, and Preferred Term	Safety Population
Table 14.3.4.1	Clinical Laboratory Data – Blood Chemistry – DSP-5423P Treatment Phase	Safety Population
Table 14.3.4.2	Clinical Laboratory Data – Blood Chemistry – DSP-5423 (tablet) Treatment Phase	Subjects treated with DSP-5423 (tablet)
Table 14.3.4.3	Clinical Laboratory Data – Hematology – DSP-5423P Treatment Phase	Safety Population
Table 14.3.4.4	Clinical Laboratory Data – Hematology – DSP-5423 (tablet) Treatment Phase	Subjects treated with DSP-5423 (tablet)
Table 14.3.4.5	Clinical Laboratory Data – Urinalysis – DSP-5423P Treatment Phase	Safety Population
Table 14.3.4.6	Clinical Laboratory Data – Urinalysis – DSP-5423 (tablet) Treatment Phase	Subjects treated with DSP-5423 (tablet)

No	Title	Population
Table 14.3.4.7	Markedly Abnormal Post-Baseline Clinical Laboratory Values – DSP-5423P Treatment Phase	Safety Population
Table 14.3.5.1	Vital Signs and Body Weight – DSP-5423P Treatment Phase	Safety Population
Table 14.3.5.2	Vital Signs and Body Weight – DSP-5423 (tablet) Treatment Phase	Subjects treated with DSP-5423 (tablet)
Table 14.3.5.3	Markedly Abnormal Post-Baseline Vital Signs – DSP-5423P Treatment Phase	Safety Population

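### Under the SAP table list, Cohort 1 tablet-phase and patch-phase adverse events are counted in different subjects, and the SAP text contradicts that list, so the switching objective has no like-for-like AE pair

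*SAP*

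**What the plan says.** A secondary objective in SAP 4.2 is "To evaluate the safety and effectiveness of switching from DSP-5423 (tablet) to DSP-5423P". Cohort 1 supplies that evidence, with 6 weeks on tablet followed by 52 weeks on patch.

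For tablet-phase adverse events, SAP 9.12.1 says: "Adverse events and extrapyramidal adverse events started during DSP-5423(tablet) treatment period of Cohort 1, meaning Tab-Day 1 to Day -1 will be summarized". It gives a time window but no population. SAP 10.2 lists the first of the resulting tables, 14.3.1.21, as "Adverse Events in DSP-5423 (tablet) Treatment Phase by System Organ Class and Preferred Term", with all tablet-treated subjects in the population column. Table 14.3.1.22 (extrapyramidal AEs) has the same population.

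Patch-phase AE tables are listed on the Safety Population, which SAP 6.1 defines as "Subjects with at least one application of DSP-5423P". In Cohort 1 that means switchers only.

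The body of the SAP differs from the list. Section 9 opens with "All efficacy, safety and other analysis are based on Safety Analysis Population, and PK analysis are based on PK analysis population", and section 9.12 says "Safety analysis will be performed for each cohort and cohort total based on safety population, besides C-SSRS summaries only for each cohort". Neither makes an exception for the tablet phase. Section 9.7 sets the overall-period antiparkinson denominator at the Safety Analysis Population, yet Table 14.1.7.13 is listed on tablet-treated subjects. Section 6 defines only the safety and pharmacokinetic populations.

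**The concern.** The disposition plan in SAP 9.1 has a category for Cohort 1 subjects who took the tablet but never went on to the patch. Under the table list their AEs count in the tablet-phase tables, and they are absent from every patch-phase table. No listed table gives tablet-phase AEs or extrapyramidal AEs in switchers alone.

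No formal tablet-versus-patch contrast is planned, so the descriptive tables are the evidence on switching. A reader will naturally set the 6-week tablet table beside the Week 1 to 6 onset window that SAP 9.12.1 provides for the patch. If leavers had more AEs than switchers, part of any fall in AE rates would come from who is counted. If the body text governs instead, that mismatch disappears, but leavers' AEs then drop out of all summary tables and remain only in listings.

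**Working it through.** The plan states no figure on this point. Its one derived number, enrolment of 200 in Protocol 15.1, reproduces as 100 / (1 - 0.5) = 200 and is unaffected.

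**Which population applies**
- SAP 9.12.1: no population named. Its window ends at Day -1, and Day 1 (SAP 8.3) is the first patch day, so the window has no stated end for someone who never had a patch.
- SAP 9 and 9.12: Safety Population, so switchers only in Cohort 1.
- SAP 10.2: all tablet-treated subjects.
- SAP 9.7: visit denominators are subjects receiving the drug in that period, and the overall denominator is the Safety Analysis Population. Overall is the only tablet-phase row, so this conflicts with Table 14.1.7.13.

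The documents do not say which governs.

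**Size if the table list governs**

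Let d be the share of tablet takers who never apply a patch, p the 6-week AE risk in switchers on tablet, and q the AE risk on tablet in leavers. Suppose the switch changes nothing, so the patch Week 1-6 risk is also p.

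Tablet-table rate T = (1 - d)p + dq, so T - p = d(q - p).

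All three inputs are assumptions. The Protocol 15.1 remark that about half of subjects ended early in previous tablet studies does not give d for a 6-week phase.

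| p | d | q | T | T - p (points) |
|---|---|---|---|---|
| 0.30 | 0.1 | 0.5 | 0.32 | +2 |
| 0.30 | 0.2 | 0.8 | 0.40 | +10 |
| 0.30 | 0.3 | 1.0 | 0.51 | +21 |
| 0.30 | any | 0.3 | 0.30 | 0 |
| 0.30 | 0.2 | 0.2 | 0.28 | -2 |
| 0.50 | 0.2 | 0.8 | 0.56 | +6 |
| 0.50 | 0.2 | 0.2 | 0.44 | -6 |

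Restricting the tablet table to switchers sets d = 0 and removes the term.

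**Whole-phase tables**

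These compare 6 weeks with 52. At a constant hazard and p = 0.30, the 52-week risk is 1 - 0.70^(52/6) = 0.955. With exponential dropout reaching 50% by Week 52, the AE hazard is h = -ln(0.70)/6 = 0.0594 per week and the dropout hazard is l = ln(2)/52 = 0.0133. The risk is then h/(h + l) × (1 - exp(-52(h + l))) = 0.80. Both exceed the largest tablet figure above for p = 0.30, which is 0.51. In these scenarios the whole-phase comparison runs against the patch.

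**Two further features of the Week 1-6 comparison**

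Neither is a population effect, but both push the same way. Protocol 7.2.2 reports for the tablet that "most of the common/frequent adverse events, including akathisia, tremors, insomnia, and increased blood prolactin, have been observed in 4 weeks after administration initiation", so first-exposure events fall mainly in the tablet phase. Under SAP 7.2.1, a tablet-phase AE that continues without worsening counts only to the tablet phase.

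**The case against.** The case against is substantial.

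- **The body text may govern.** Sections 9 and 9.12 point to switchers, under which the mismatch vanishes. This stands as a limit: the firm defect is an unreconciled SAP, not a settled biased analysis. It does not remove the need to act, because leavers' AEs would then appear in no summary table.
- **Same-subject readings already exist for the scales.** In Cohort 1 the patch-phase baseline is normally the Tab-Week 6 visit (SAP 8.4 and the assessment schedule). Change from that baseline in PANSS, CGI-S and DIEPSS therefore compares patch with end of tablet in the same people, and the figures covering the entire study are also listed on the Safety Population. This stands.
- **Antiparkinson use is largely covered.** SAP 9.7 gives Day -1 and then Weeks 1-2, 3-4 and 5-6, with the Safety Analysis Population as the Day -1 denominator. This also stands, apart from the conflict over the overall tablet-period denominator.
- **Direction and size are not in the documents.** This is correct. Protocol 7.2.3 says antipsychotics are often stopped for adverse reactions or lack of efficacy, which makes q above p plausible. But leavers also have shorter exposure, which works the other way.
- **No contrast is planned, and reporting tablet AEs in everyone exposed is proper safety reporting.** Agreed, so those tables should stay. It does not supply the missing switcher-only pair.

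**Conclusion.** The point holds for adverse events and extrapyramidal adverse events. The SAP gives two populations for the same tablet-phase tables and leaves one of them undefined. If the table list is followed, no like-for-like AE comparison supports the safety half of the switching objective. In the length-matched reading the listed tables are likely to favour the patch if leavers had more AEs than switchers. The amount is d(q - p), about +2 to +21 points in the p = 0.30 illustrations with q above p, and zero or negative otherwise. Every input is assumed.

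A reader might infer that the whole tablet-versus-patch reading is biased towards the patch, and that AE rates, DIEPSS and antiparkinson use will appear to improve even if the switch changes nothing. The documents do not support that. The scales and, largely, antiparkinson use have same-subject readings. The sign for AEs depends on q against p. Whole-phase AE tables carry 52 weeks of patch exposure against 6 of tablet.

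**What to change.** 1. Define the tablet-treated population in SAP section 6, and state where the tablet-phase AE window ends for a subject with no Day 1.
2. Reconcile sections 9, 9.7 and 9.12 with the table list, including the overall tablet-period antiparkinson denominator against Table 14.1.7.13.
3. Keep Tables 14.3.1.21 and 14.3.1.22 on all tablet-treated subjects.
4. Add versions of both restricted to Cohort 1 subjects in the Safety Population. Show them beside the Cohort 1 patch Week 1-6 first-onset results (Tables 14.3.1.6 and 14.3.1.25).
5. State that the AE part of the switching objective is read from that pair. Note beside it that AEs cluster early after first blonanserin exposure, and that tablet AEs continuing without worsening count only to the tablet phase. Restricting the population removes neither effect.

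The cost is SAP wording and a re-run of existing programs on a subset. No new data are needed; the downside is a few extra tables.
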